**Effect of Chronic Exenatide Therapy on Beta Cell Function and Insulin Sensitivity in T2DM**

## **Study A.**

**Subjects:** 80 T2DM subjects (age = 18-70 years; BMI = 21-45 kg/m^2; male or female) according to the ADA criteria will participate in the study. Subjects must be drug naïve and/or on a stable dose (more than 3 months) of metformin and/or sulfonylurea and have HbA1c >7.0% and <10.5%. Subjects taking drugs known to affect glucose metabolism (other than metformin and sulfonylurea) will be excluded. Other than diabetes, subjects must be in good general health as determined by physical exam, medical history, blood chemistries, CBC, TSH, EKG and urinalysis. Only subjects whose body weight has been stable ( $\pm$  3 lbs) over the preceding three months and who do not participate in an excessively heavy exercise program will be included. Individuals with evidence of proliferative diabetic retinopathy, plasma creatinine >1.4 females or >1.5 males will be excluded. Diabetic subjects will be recruited from the South Texas Veterans Health Care System and Texas Diabetes Institute (TDI) in San Antonio (Deputy Director = [name]). TDI is the largest institute in the United States that provides comprehensive care for ~ 10,000 unduplicated T2DM patients. Therefore, we do not anticipate any problem in recruiting the required number of patients for this study.

**Study design:** After screening, eligible subjects will receive a measurement of endogenous glucose production (EGP) with a prime-continuous infusion of 3-H-glucose. The EGP measurement will be performed in the morning after a 10-12 hour overnight fast and will last 8.5 hours (from 6 AM to 2:30 PM). After a 3.5-hour tracer equilibration period, subjects (20 per group) will receive one of the following medications: (i) placebo; (ii) exenatide 5 ug subcutaneously; (iii) dapagliflozin (10 mg); and (iv) dapagliflozin 10 mg plus exenatide 5 ug (see flow diagram on page 11). Following the test medication at 9:30 AM, blood samples will be drawn every 10-20 minutes for an additional 5 hours and plasma glucose, insulin, C-peptide, glucagon concentrations and glucose specific activity will be measured. One-two weeks after the EGP measurement, participants will come back for the Double Tracer Oral Glucose Tolerance Test (DT-OGTT).

**Visit 1: Screening.** Medical history will be obtained and physical exam will be performed. Blood will be drawn for FPG, routine blood chemistries, CBC, lipid profile, HbA1c, and thyroid function. Urinalysis, EKG, albumin/creatinine ratio and pregnancy test will be performed.

**Visit 2: Endogenous Glucose Production Measurement (EGP):** The rate of endogenous glucose production will be measured with 3-H-glucose infusion. [3-H]-glucose infusion will be started at 6 AM and continued until 2:30 PM (5 hours after drug administration). At 6 AM a catheter will be placed into an anticubital vein and a prime (40 uCi x FPG/100)- continuous (0.4 uCi) infusion of [3-H]- glucose will be started and continued until 2:30 PM. Participant's hand will be placed in a box heated to 50-60°C (122-140°F). Baseline blood samples will be obtained at -210, -60, -50, -45, -40, -35, -30, -20, -10, and 0. After 3.5 hours of tracer equilibration blood samples will be obtained every 10-20 minutes from 9:30 AM to 2:30 PM. Plasma glucose, insulin, C-peptide, glucagon, concentrations, and [3-H]-glucose specific activity will be measured. Urine will be collected from 6 to 9:30 AM and from 9:30 AM to 2:30 PM. Urinary volume and glucose concentration will be measured and urinary glucose excretion rate calculated. The study will end at 2:30 PM.

**Visit 3: Double Tracer Oral Glucose Tolerance Test (DT-OGTT):** Within one to two weeks after the measurement of EGP, all subjects will have a 5-hour DT-OGTT with measurement of plasma glucose, insulin (I), C-peptide (CP), and glucagon concentrations at -180, -60-, -50-, -45, -40, -35, -30, -20, -10, 0 and every 15-30 minutes thereafter to obtain a measure of overall glucose tolerance, insulin secretion ( $\Delta$ CP0-120/ $\Delta$ G0-120), insulin sensitivity (Matsuda index [MI]), beta cell function, ( $\Delta$ CP0-120/ $\Delta$ G0-120 x MI), and suppression of plasma glucagon concentration (64). At 7 AM a catheter will be placed into an anticubital vein and a prime (25 uCi x FPG/100)- continuous (0.25 uCi) infusion of [3-H]- glucose will be started and continued until 3 PM. Urine will be collected from 7 to 10 AM and from 10 AM to 3 PM. Urinary volume and glucose concentration will be measured and urinary glucose excretion rate calculated. The study will end at 3 PM.

HbA1c will be measured twice, once on the day of the DTOGTT and once on the day of the EGP measurement.

**Data Analysis and Statistical Methods:** The **primary end point** of the study is the change in EGP during **Study A**. The difference in the rate of EGP during the last hour of the study (i.e. from 240-300 minutes) between drug-treatment and placebo-treatment studies represents the effect of drug treatment on EGP. The difference in EGP will be compared among the 3 drug treatments (exenatide, dapagliflozin, and exenatide plus dapagliflozin) with ANOVA. Post hoc testing will be performed with a Bonferroni correction for multiple

comparisons. The following primary comparison will be performed: (i) the change in EGP above baseline following dapagliflozin alone versus dapagliflozin/exenatide. The following secondary comparisons will be made: (i) the change in EGP above baseline following exenatide alone versus dapagliflozin/exenatide and (ii) the change in EGP above baseline following dapagliflozin alone, exenatide alone, and dapagliflozin/exenatide versus the change in EGP following placebo. Between group comparisons will be made with repeated measures ANOVA with time and treatment group as factors.

**Other secondary end points** will be: (i) the decrement in the fasting plasma glucose conc at the end of the study compared to baseline, (ii) change in plasma glucagon conc at the end of the study compared to baseline; and (iii) change in plasma insulin conc at the end of the study compared to baseline. Secondary end points will be compared using the same statistical methods described for the primary end point.

**Anticipated Results and Data Interpretation.** Consistent with our published data (10), we anticipate that EGP will decrease progressively following placebo administration while, after an initial decline, EGP will increase progressively following dapagliflozin. We anticipate that plasma glucagon conc will increase and plasma insulin concentration will decrease following dapagliflozin administration. We anticipate that a single administration of exenatide will cause an increase in plasma insulin conc and a decrease in plasma glucagon conc compared to placebo. The increase in plasma insulin and decrease in plasma glucagon conc following exenatide administration will result in a greater decline in both EGP and fasting plasma glucose conc compared to placebo. Most importantly, we anticipate that the increase in plasma glucagon conc, the decrease in plasma insulin conc, and rise in EGP following dapagliflozin administration will be prevented, at least in part, if not totally, when exenatide is co-administered with dapagliflozin. Therefore, we anticipate an additive, even synergistic, decrease in plasma glucose conc and EGP following co-administration of dapagliflozin plus exenatide compared to either drug alone.

**Sample Size Calculation:** In our published results (10), the difference in the rate of basal EGP during the last hour of EGP measurement in dapagliflozin-treated and placebo-treated individuals was  $0.70 \pm 0.34$  (mean  $\pm$  SD). To detect a 50% decrease in the difference at alpha = 0.005 ( $=0.5/10$ ) (split alpha for up to 10 multiple comparisons and a Bonferroni correction) in exenatide plus dapagliflozin versus dapagliflozin alone, we computed that 17 subjects in each group provided 90% power. To ensure 17 completers assuming 15% lost to follow-up, we have set the sample size at 20 ( $=17/0.85$ ) in each group.

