### **Study B (see flow sheet below)**

Following the measurement of endogenous glucose production [EGP] in Study A, and after the double tracer OGTT visit, subjects who receive Byetta will be started on Byetta, 5 ug sc bid, and they will return for a follow up visit in 7 days (visit 4) at which time the Byetta will be increased to 10 ug sc bid, if tolerated. Subjects will return at days 14, 21, and 28 (visits 5, 6, and 7). If the Byetta dose cannot be increased to 10 ug bid because of side effects on the day 7 visit, the dose will be advanced on the subsequent visit (i.e., day 14 or 21 or 28), side effects permitting. On the day 28 visit the Double Tracer OGTT will be repeated with Byetta dosing at time zero of study (Visit 7).

Subjects who received dapagliflozin will continue on dapagliflozin, 10 mg/day, and will return for follow up visits at days 7, 14, and 21. At the day 28 visit the the DT-OGTT will be repeated. On the day of DT-OGTT, dapagliflozin will be given in the morning prior to the study. Note that this group will not receive Byetta and, thus, will allow us to determine how long the effect of dapagliflozin to increase EGP persists.

Subjects who received dapagliflozin plus Byetta will continue on dapagliflozin and Byetta, and will return for follow up visits at days 7, 14, and 21. At the day 28 visit the DT-OGTT will be repeated. On the day of the DT-OGTT, dapagliflozin will be given in this group will allow us to determine whether the ability of Byetta to inhibit the paradoxical rise in EGP observed with dapagliflozin can be blocked on a chronic basis.

Subjects who received the placebo will not be continued forward. However, these subjects will be allowed to be randomized to the Byetta alone, dapagliflozin alone, or Byetta/dapagliflozin groups.

**Visits 4, 5 and 6: Brief Follow Up Visits** for interim medical history and compliance with the treatment regimen a BMP will be done to check on your kidney function.

**Visit 7: Double Tracer OGTT** will be performed as per **Visit 3**.

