### **Study C (see flow sheet below).**

Following completion of the OGTT (Visit 7), subjects will be started on Bydureon, 2 mg sc per week. Subjects will return of interim follow up visits at weeks 6, 8, 10, 13-14, (visits 8, 9,10, 11. During the weeks 16-18 (visit 12),subjects will have a repeat Double Tracer OGTT (visit 12) will be performed..

**Visits 8, 9, 10, and 11. Brief Follow Up Visits** for interim medical history and compliance with the Bydureon regimen.

**Visit 12: Double Tracer OGTT** will be performed as per **Visit 3**.

The treatment period could be extended based upon the circumstances (based upon the situation of COVID-19 pandemic) until the repeat studies are completed.

**Data Analysis:** In **Study B**, we anticipate that dapagliflozin and Byetta will produce similar reductions in HbA1c and that the combination of dapagliflozin plus Byetta will produce an additive/near-additive reduction in A1c. We anticipate that both dapagliflozin and Byetta monotherapy will produce significant weight loss and that the combination will produce an additive, even synergistic, effect on weight loss.

We anticipate that that the dapagliflozin-induced rise in EGP will persist after 1 month in T2DM patients receiving dapagliflozin monotherapy even though both beta cell function and peripheral insulin sensitivity improve. We expect that Byetta-treated T2DM patients will experience a reduction in both fasting and postprandial plasma glucose levels during the DT-OGTT, markedly enhanced beta cell function, improved peripheral tissue insulin sensitivity, and reduced fasting and postprandial plasma glucagon concentrations during the DT-OGTT. In T2DM patients receiving combined Byetta/dapagliflozin therapy, we hypothesize that exenatide will block the dapagliflozin-induced rise in glucagon secretion and overcome the dapagliflozin-induced decrease insulin secretion, resulting in a greater suppression of EGP. Because we anticipate that Byetta will offset the negative effects of dapagliflozin on EGP and on insulin and glucagon secretion, we expect that the decline in fasting and postprandial glucose concentrations during the DT-OGTT will be enhanced in T2DM subjects receiving combination Byetta/dapagliflozin therapy.

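### Background metformin and sulfonylurea use is mixed within arms of 20, but is neither a stated stratification factor nor a covariate in the EGP, glucose, insulin and glucagon comparisons

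*Combined protocol and SAP*

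**What the plan says.** All references are to the combined protocol and SAP.

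- **Study A, Subjects.** Entry is open to untreated and treated patients: "Subjects must be drug naïve and/or on a stable dose (more than 3 months) of metformin and/or sulfonylurea and have HbA1c >7.0% and <10.5" per cent. The next rule names the same two drugs as the exception among glucose-active drugs: "Subjects taking drugs known to affect glucose metabolism (other than metformin and sulfonylurea) will be excluded".
- **Study A, Study design.** Allocation is described only by "subjects (20 per group) will receive one of the following medications". No allocation method or stratification factor is given.
- **Study A, Data Analysis and Statistical Methods.** For the primary endpoint, "The difference in EGP will be compared among the 3 drug treatments (exenatide, dapagliflozin, and exenatide plus dapagliflozin) with ANOVA". In addition, "Between group comparisons will be made with repeated measures ANOVA with time and treatment group as factors". The secondary endpoints (fasting glucose, glucagon, insulin) use the same methods. No covariate is named. The primary comparison is the change in EGP from baseline, dapagliflozin alone against the combination.
- **Study B.** Randomisation is mentioned only for placebo subjects who continue: "However, these subjects will be allowed to be randomized to the Byetta alone, dapagliflozin alone, or Byetta/dapagliflozin groups". Visits 4-6 cover interim history, compliance with the regimen and a kidney-function check.
- **Study C.** Visits 8-11 are "Brief Follow Up Visits for interim medical history and compliance with the Bydureon regimen". Neither Study B nor Study C says that background drug and dose are recorded at visits, or how a change would enter the analysis.

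**The concern.** Each arm may hold untreated, metformin-treated, sulfonylurea-treated and dual-treated patients. The plan itself classes both drugs as acting on glucose metabolism, and its outcomes are EGP, glucose, insulin and glucagon. If patients on one background respond differently to the test drug over the five hours, two things follow. The variation between background groups stays in the error term, which makes the test less sensitive. And with 20 per arm, the arms may differ in background mix by chance, so part of the observed contrast would reflect that mix.

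Background therapy is established at entry, so both effects can be reduced with information that the trial already has. The primary contrast is a mechanistic claim about exenatide offsetting the EGP rise after dapagliflozin. An unadjusted result from arms with visibly different background would be hard to defend.

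**Working it through.** **Inputs from the documents** (Study A, Study design and Sample Size Calculation): 20 subjects per arm; 17 completers; reference difference 0.70 with SD 0.34; a 50% reduction to be detected. No unit is printed.

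**Inputs not in the documents, assumed here:** share on sulfonylurea p = 0.3 to 0.5; effect g of background use on the EGP change of 0.1, 0.2 or 0.35; independent random allocation; 0.34 read as the between-subject SD of the EGP change. The top value of g equals the whole effect that the trial is sized for, so it is an upper bound for illustration.

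**1. The plan's own figures.** Target difference = 0.50 × 0.70 = 0.35. Enrolment = 17/0.85 = 20, which agrees. The 17 itself is not reproduced: a two-sample normal formula with 0.35, 0.34, two-sided alpha 0.005 and 90% power gives 32 per group. That is a separate matter and nothing below depends on it.

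**2. Chance imbalance between two given arms.** Users per arm follow Binomial(20, p).

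| | p = 0.3 | p = 0.5 |
|---|---|---|
| SD of the difference in proportions, √(2p(1−p)/20) | 0.145 | 0.158 |
| Mean absolute difference, about 0.8 × SD | 0.12 | 0.13 |
| P(difference ≥ 20 points), exact | 0.226 | 0.268 |
| P(difference ≥ 25 points), exact | 0.119 | 0.154 |

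**3. Shift of the unadjusted contrast** = imbalance × g, also as a share of 0.35.

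| Imbalance | g = 0.1 | g = 0.2 | g = 0.35 |
|---|---|---|---|
| 0.12 (typical) | 0.012 (3%) | 0.024 (7%) | 0.042 (12%) |
| 0.20 | 0.020 (6%) | 0.040 (11%) | 0.070 (20%) |
| 0.25 | 0.025 (7%) | 0.050 (14%) | 0.088 (25%) |

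**4. Comparison with sampling error.** Standard error of the contrast = 0.34 × √(2/20) = 0.108 with 20 per arm, and 0.34 × √(2/17) = 0.117 with 17. Every shift in step 3 is below one standard error.

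**5. Precision gained by adjustment** for one binary factor at p = 0.5: residual SD = √(0.34² − g² × 0.25).

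- g = 0.1: √(0.1156 − 0.0025) = 0.336, variance down 2%.
- g = 0.2: √(0.1156 − 0.0100) = 0.325, variance down 9%.
- g = 0.35: √(0.1156 − 0.0306) = 0.292, variance down 26%.

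**6. Cost in degrees of freedom.** For the ANOVA of the three drug arms, error degrees of freedom fall from 60 − 3 = 57 to 55.

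**7. Which study each gap touches.** The Study A endpoint comes from one 8.5-hour session after a single administration, so a change of background therapy during follow-up cannot enter it. Study B (28 days) and Study C (weeks 16-18, extendable) are the only parts where background could change between measurements.

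**The case against.** The strongest reply is that random allocation already deals with this. Imbalance then has no preferred direction and is covered by the error rate of the test. Analysing change from baseline also removes any stable difference in EGP level between background groups. The typical imbalance is only about 12-13 points, and the size of the effect is assumed throughout.

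Most of this stands. It limits the point to lost precision and to imbalance in the one sample obtained. It does not remove the point. Change from baseline does not remove a different response by background, and the protection from randomisation is assumed here because the plan states no allocation method for Study A.

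A reader might infer more, and the documents do not support it:

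- **Systematic confounding of the primary contrast.** This would need allocation related to background. The plan is silent on the method; silence does not show that allocation was non-random.
- **Background drift biasing the primary endpoint.** Step 7 rules this out.
- **Background doses being lowered mainly in the exenatide arms.** No passage describes background dose reduction in any arm. For Study C, the text that starts subjects on Bydureon does not clearly limit it to particular arms.
- **Background changes going unnoticed.** Interim history is taken at each follow-up visit. Recording of drug and dose is unspecified, but it is not excluded.

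**Conclusion.** The point holds as a moderate, inexpensive improvement. Background therapy is known at entry, is treated by the plan as relevant to glucose metabolism, and appears in neither the stated allocation nor the stated models. Given random allocation and 30-50% sulfonylurea use, about one trial in four would show a gap of at least 20 points between the two arms of the primary comparison. What that does to the result depends on an effect that the documents do not give. Over the assumed range of 0.1-0.35, such a gap shifts the contrast by 6-20% of the 0.35 target, always less than one standard error, and adjustment lowers the residual variance by 2-26%.

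These figures do not support calling the planned analysis invalid or the primary comparison confounded. The absence of any on-study provision for background therapy is a reporting gap in Studies B and C only.

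**What to change.** 1. **Covariates.** In Study A, Data Analysis and Statistical Methods, prespecify background sulfonylurea (yes/no) and metformin (yes/no) as covariates in the models for EGP, glucose, insulin and glucagon. Do the same for the between-arm EGP, insulin and glucagon comparisons of Studies B and C, for which a model still has to be written down.
2. **Allocation.** State the Study A method. Where allocation is still open, stratify by sulfonylurea use (yes/no), including when placebo subjects are randomised in Study B. One binary factor is enough; a full cross of background groups would be too sparse with 20 per arm.
3. **Recording in Studies B and C.** Record background drug and dose at Visits 4-6 and 8-11 and at the DT-OGTT visits, and report changes by arm. This imposes no rule on background treatment. Do not base inference on an analysis that drops DT-OGTTs done after a change: that selects on an event after allocation and can itself create bias.

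Cost: two degrees of freedom, one stratification factor and one case report form line per visit. No additional subjects are needed. If recruitment is complete, items 1 and 3 can still be done as far as the records allow, with item 1 fixed before the data are examined by arm.

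### Study A names two methods and two metrics for the EGP comparison without saying which is primary, and leaves the times and tested term of the repeated-measures ANOVA open; a single ANCOVA on last-hour EGP would settle it.

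*Combined protocol and SAP*

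**What the plan says.** All of this is in the combined protocol and SAP, Study A.

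- **First method and metric** (Data Analysis and Statistical Methods). The drug effect is the EGP difference between drug and placebo "during the last hour of the study (i.e. from 240-300 minutes". That difference is compared among the three drug arms by ANOVA, with Bonferroni-corrected post hoc tests.
- **Primary comparison** (same section). It is "the change in EGP above baseline following dapagliflozin alone versus dapagliflozin/exenatide". This is a different metric, change from baseline, and the sentence carries no time window.
- **Second method** (same section). "Between group comparisons will be made with repeated measures ANOVA with time and treatment group as factors". The section does not say which times enter, or whether the group effect or the group-by-time term is the test.
- **Secondary end points.** They are stated at the end of the study against baseline, for example "the decrement in the fasting plasma glucose conc at the end of the study compared to baseline". The plan adds: "Secondary end points will be compared using the same statistical methods described for the primary end point".
- **Sample size** (Sample Size Calculation). It starts from the last hour: "the difference in the rate of basal EGP during the last hour of EGP measurement in dapagliflozin-treated and placebo-treated individuals was" 0.70 with SD 0.34. The target is a 50% decrease in that difference for the combination versus dapagliflozin alone.
- **Expected course** (Anticipated Results and Data Interpretation). "after an initial decline, EGP will increase progressively following dapagliflozin", and the "rise in EGP following dapagliflozin administration will be prevented, at least in part, if not totally, when exenatide is co-administered with dapagliflozin".
- **Baseline and dosing.** The Study design paragraph puts the test medication at 9:30 AM, and Visit 2 lists baseline samples through time 0. The 3-3H-glucose turnover table places dapagliflozin at -30 minutes.

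**The concern.** The primary comparison is a between-group comparison, so as written it falls under the repeated-measures ANOVA as well as under the earlier ANOVA. The two need not estimate the same quantity. The sample size concerns one number, the last-hour difference. A group effect averaged over the whole post-dose period is a different number unless the effect is constant, and a group-by-time term answers a different question again.

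Because the plan does not choose, the times and the term could be settled after the data are seen. The secondary end points inherit the same gap, since they use the same methods.

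**Working it through.** **1. The plan's own figure.** Inputs from the Sample Size Calculation: difference 0.35 (50% of 0.70), SD 0.34, alpha 0.005, power 90%, 17 per group. The formula is n = 2(z₁ + z₂)²SD²/δ², taken two-sided.

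- 0.34 as the SD of a difference (per-arm SD 0.34/√2 = 0.24): (2.807 + 1.282)² × (0.34/0.35)² = 15.8, so 16 per group, or 18 with the t distribution. Power at 17 is 0.88. This is close to the stated 17.
- 0.34 as a per-arm SD: 31.5, so 32 per group, or 34 with t.

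Which SD is meant is a separate question. Here it matters only that the planned effect is a last-hour effect. The sample sizes in step 3 are therefore relative to a last-hour test.

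**2. How much of the last-hour effect an all-times group effect captures.** The turnover table has 30 tracer samples: 9 at or before time 0 and 21 after it. Seven of the 21 lie in 240-300 minutes (240, 260, 280, 285, 290, 295, 300). The ratio is the mean effect over the 21 times divided by the mean over those 7. The profiles are assumptions, because the documents give no time course.

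| Assumed profile of the group difference | Mean over 21 / mean over last 7 | Ratio |
|---|---|---|
| Constant | 1 / 1 | 100% |
| Linear to 120 min, then flat | (17.5/21) / 1 | 83% |
| Linear from 0 | (3540/21) / (1950/7) = 168.6 / 278.6 | 61% |
| Linear from 60 min | (2370/21) / (1530/7) = 112.9 / 218.6 | 52% |
| Linear from 120 min | (1440/21) / (1110/7) = 68.6 / 158.6 | 43% |

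**3. Effect on sample size.** Averaging 21 samples instead of 7 also lowers the variance. I assumed a between-subject share of variance of 0.5-0.9 and an exponential serial correlation with a time constant of 30-120 minutes. The variance of the 21-sample mean is then 0.75-0.96 times that of the last-hour mean. Relative sample size is the variance ratio divided by the squared effect ratio, in the order of the table: 0.75-0.96, 1.1-1.4, 2.1-2.6, 2.8-3.6 and 4.0-5.2. The all-times average gains if the effect is constant and loses under the other profiles.

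**4. Group-by-time over the 21 times.** Its null hypothesis is parallel curves. A constant drug difference satisfies that null, and a difference at any time can break it. It is therefore not a test of the last-hour contrast, whatever its power.

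**5. ANCOVA against a change score.** Let k be the post-dose SD divided by the baseline SD, and rho the correlation between baseline and last-hour EGP. Neither is in the documents. The residual variance ratio is k²(1 − rho²)/(k² + 1 − 2k·rho), which is (1 + rho)/2 when k = 1.

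| k | rho 0.3 | rho 0.5 | rho 0.7 |
|---|---|---|---|
| 1 | 0.65 | 0.75 | 0.85 |
| 1.25 | 0.784 | 0.893 | 0.981 |
| 1.5 | 0.871 | 0.964 | 0.998 |

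The variance saving is 15-35% with equal SDs, 2-22% at k = 1.25 and 0-13% at k = 1.5.

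**6. Baseline.** If dapagliflozin is taken at -30 minutes, 3 of the 9 baseline tracer samples (-20, -10 and 0) follow it. A mean shift d in those three moves a nine-sample mean by 3d/9 = d/3. Both arms of the primary contrast receive dapagliflozin, so the shift cancels there in expectation. It does not cancel against placebo or exenatide alone.

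**The case against.** The strongest reply is that the plan reads coherently as it stands. The window follows directly on the naming of the primary end point, the first ANOVA contains both arms of the primary comparison, and the sample size is set for that comparison on the last hour. The secondary end points contrast end of study with baseline by the same methods, so time in the repeated-measures ANOVA may mean just those two levels. Its group-by-time term is then the ordinary change-score test. This is a fair reading and much of it stands, but the text does not select it.

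Several stronger readings should be resisted:

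- A reader might infer that the plan has no last-hour analysis. It has one, in the first ANOVA, and the window is implied for the primary comparison.
- A reader might infer that a two-level group effect, which averages baseline in, could be the primary test and would dilute the effect. The stated metric is change above baseline, which points away from that term, so I give it no weight.
- A reader might infer that the group-by-time term loses power. That is not shown. With 17 per group, alpha 0.005, a per-arm SD of 0.34 and a mid-range correlation setting (subject share 0.7, 60 minutes), simulation gives about 0.55-0.96 over the non-constant profiles, against about 0.50 for the last-hour test. Other settings give lower or higher values. The objection is to what the term tests.
- A reader might infer that baseline is wholly undefined, or that dosing time biases the primary contrast. Visit 2 lists the baseline samples, and the timing shift affects both dapagliflozin arms alike.

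Nor is a change score invalid. ANCOVA is preferred for precision, and a prespecified last-hour contrast from a mixed model would also serve.

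**Conclusion.** The point holds as a gap in specification with a concrete better method available. Two methods and two metrics are named, none is designated primary, and the times and tested term of the repeated-measures ANOVA are missing.

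The size depends on the choice later made. With a last-hour change score nothing is lost except some precision. With the group effect over all post-dose times, the estimate is 83% of the last-hour effect under the assumed plateau and 43-61% under the assumed linear profiles. The expected progressive rise after dapagliflozin, prevented by exenatide, suggests a difference that grows with time but does not establish its shape. If the effect were constant, nothing would be lost.

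The precision gain from ANCOVA rests on assumed correlations and SD ratios. Apart from one degree of freedom, it is at least as precise as the change score.

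**What to change.** Name one primary analysis for Study A: ANCOVA on each subject's mean EGP over 240-300 minutes (the seven scheduled tracer samples), with four-arm treatment as factor, baseline EGP as covariate, and dapagliflozin versus dapagliflozin/exenatide as the primary contrast. Take the secondary contrasts, including those with placebo, from the same model. Keep the repeated-measures ANOVA as supportive, and state its times and the term to be reported.

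If the change score is kept instead, define it as mean EGP over 240-300 minutes minus mean baseline EGP, and name its between-arm contrast as the only primary test.

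Reconcile the Study design paragraph and Visit 2 (medication at 9:30 AM, baseline through time 0) with the turnover table (dapagliflozin at -30 minutes). Then define baseline EGP from named samples drawn before any study drug.

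The change is to wording only. It needs no new samples and costs one degree of freedom for the covariate.
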